**Equation 1.**

$$Change_{itk} = \beta_0 + \delta X_{itk} + \omega Pre_{itk} + \beta X_i + \gamma_{0ik} + v_{0k} + \epsilon_{ik}$$

i = Participant Subscript, 1, ..., N

k = Cluster Subscript, 1, ..., K

t = time period, 1 = Control, 2 = Intervention

Changeitk = Change in efficacy outcome over period t

Preitk = Pre measurement from period t

For Control period: Pre = Q1, Change = Q2 - Q1

For Intervention period: Pre = Q2, Change = Q3 - Q1

xitk = Binary indicator for intervention for patient i in k at time t

Xi = Vector of covariates for participant i

$\beta_0$  = General intercept of the model

$\delta$  = Intervention effect (coefficient of xitk)

$\omega$  = Baseline measurement adjustment effect (coefficient of Preitk)

$\beta$  = Vector of coefficients associated with covariates in Xi

$\gamma_{0ik}$  = Participant-specific random intercept with mean zero and variance  $\sigma_{\gamma}^2$

$v_{0k}$  = Cluster-specific random intercept with mean zero and variance  $\sigma_v^2$

$\epsilon_{itk}$  = Random error with mean zero and variance  $\sigma_{\epsilon}^2$

**Aim 3 - Exploratory Feasibility Analysis:** To explore the feasibility of obtaining online consent for research access to CP healthcare utilization records. The number of CPs who agree to access for themselves or the PLWED on Questionnaire 3 will be counted. While we will not specifically collect utilization data, the number of CPs who agree will inform the feasibility of including healthcare utilization as an outcome in a full-scale ePCT. Any differences in CP demographics between enrollees who opt-in and those who opt-out will be assessed.

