**Table 3.**

	Counts for feasibility	Use in analysis
Participants contacted	N	Total number of targeted mailings Estimate of clinic flyer distribution using print rates
Participants who enroll and are randomized into MBDC course section	a	Recruitment rate: a/N
Participants who start MBDC course	b	Participation rate: b/N, compare to a/N
Participants who complete course (6/9 modules)	c	Completion rate: c/b, used as main progression criteria Overall successful enrollment rate: c/N
Number who complete each module in real-time – k = 1, ..., 9	d k	Module specific completion rate: d k /b

Number who complete each module as a make-up session – k = 1, ..., 9	$e_k$	Module specific make-up completion rate: $e_k/b$ Compare to $d_k/b$ to assess fidelity of make-up offerings
Number who complete each questionnaire – m = 1,2,3	$f_m$	Questionnaire specific response rate: $f_m/a$ and/or $f_m/b$ if $a \neq b$

**Aim 2 - Secondary Feasibility and Efficacy Analyses:** The completeness of the CED-D-10 and ZBI-6 outcomes will be quantified by calculating the rate of CPs that respond to all items on each scale (CES-D-10: 10 items, ZBI-6: 6 items) at each assessment. The rate of completion for both scales will be presented overall and stratified by questionnaire, site, and by CP demographics. As the current study design results in a non-uniform length of the control period, the weeks between Q1 and Q2 will be recorded and summarized for the sample to better understand how the design could scale to a larger ePCT. A preliminary efficacy analysis will utilize the total scores for the CES-D-10 (range: 0 to 30) and ZBI-6 (range: 0 to 24) calculated for all completed questionnaires. Both outcomes will be summarized at each questionnaire timepoint using means and/or medians, as appropriate. Change over the control (Q2-Q1) and intervention (Q3-Q2) periods will be calculated for each CP and summarized for the sample. Descriptive summaries will be provided for responses from CP who complete the 3-month follow-up questionnaire (Q4) within the 12-month study timeframe and before the final analytic dataset is defined. These responses will not be used in any of the formal inferential analyses.

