Analysis will utilize linear mixed-models with random effects to account for clustering of data within MBDC course section as well as repeated measures within CPs to estimate the intervention effect on depressive symptoms and care-giver burden (Equation 1). In a scaled up ePCT, we expect the unit of randomization to continue to be course section, which is reflected in our choice of random effects. The model structure will be based on a standard ANCOVA used to evaluate change that adjusts for the pre-intervention measurement of the outcome variable with the post-intervention measurement as the model outcome. Each CP will contribute a pair of data points for the control period (Pre: Q1, Post: Q2) and intervention period (Pre: Q2, Post: Q3) which requires our random effects structure to account for repeated measurements within CPs. If there is no difference in change in efficacy outcomes, we expect Q2-Q1 = Q3-Q2. Each model will include covariates to adjust for possible confounding associated with CP demographics and CP history (age, race/ethnicity, socioeconomic measures, and length of caregiving). While the relative time of measurement is considered (pre/post) our analysis does not adjust for time over the course of the study, as we hypothesize any treatment effect would be time-agnostic within the year-long pilot study time frame. When an ePCT with a longer timeline is considered, this assumption will have to be revisited. A brief assessment of self-compassion and mindfulness scales outcomes will be performed using the responses collected from the “research only” section of the questionnaires. These results will help better understand the possible mechanisms between the intervention and clinical outcome for future ePCTs. These items will be removed at the conclusion of the pilot to decrease participant burden. All analysis will be performed in SAS 9.4 and significance determined using a two-sided alpha of 0.05.

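### Equation 1 defines the intervention-period outcome as Q3 - Q1, where every other statement in Section 9.5 requires Q3 - Q2

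*Combined protocol and SAP*

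**What the plan says.** All the relevant text is in Section 9.5 (Data Analyses), under Aim 2.

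- The descriptive plan says: "Change over the control (Q2-Q1) and intervention (Q3-Q2) periods will be calculated for each CP".
- The model text gives each care partner two pairs of measurements. The second pair is "intervention period (Pre: Q2, Post: Q3".
- The model text describes an ANCOVA that "adjusts for the pre-intervention measurement of the outcome variable with the post-intervention measurement as the model outcome".
- The null is stated as: "If there is no difference in change in efficacy outcomes, we expect Q2-Q1 = Q3-Q2".
- The Equation 1 legend defines Change as "Change in efficacy outcome over period t" and Pre as "Pre measurement from period t".
- The legend then gives the two periods: "For Control period: Pre = Q1, Change = Q2 - Q1", followed by "For Intervention period: Pre = Q2, Change = Q3 - Q1".

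**The concern.** In the last legend line the starting measurement is Q2, but the change is counted from Q1. Q3 - Q1 spans the waiting period and the course together, so it is not a change within the intervention period. The control line is end-of-period minus start-of-period; the intervention line is not.

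Section 9.1 justifies the design by each participant supplying both control and intervention data. The comparison depends on subtracting what happened over the wait from what happened over the course. The printed line removes that subtraction. An analyst who codes the equation as printed would fold any change over the wait into the estimated course effect, and nothing in the model output would show it. The protocol itself allows for such change: Section 7.1 plans to look for increases in symptoms between registration and the pre-course questionnaire.

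**Working it through.** **1. Which definition the text supports**

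| Statement in Section 9.5 | Implied intervention change |
|---|---|
| Per-participant change, Aim 2 | Q3 - Q2 |
| Pre/post pair, Aim 2 | Q3 - Q2 |
| Null, Aim 2 | Q3 - Q2 |
| Legend: change over the period | Q3 - Q2 |
| Legend: control line is post minus pre | Q3 - Q2, by the same pattern |
| Legend: intervention line | Q3 - Q1 |

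Nothing else in the documents supports Q3 - Q1.

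**2. Link to the ANCOVA in the text**

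The text models the post measurement and the equation models change. If Post = b0 + δx + ω′Pre, subtracting Pre from both sides gives Post - Pre = b0 + δx + (ω′ - 1)Pre. So δ is identical and the Pre coefficient falls by exactly 1. The two descriptions therefore agree when Change = Q3 - Q2. With Q3 - Q1 and Pre = Q2 the equivalence fails.

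**3. What δ estimates**

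Write D = mean(Q2 - Q1) and E = mean(Q3 - Q2). With both periods observed for everyone, δ is the difference between periods in mean Change, minus ω times the difference in mean Pre. The difference in mean Pre is D.

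- As written: mean(Q3 - Q1) - mean(Q2 - Q1) = E, so δ = E - ω_w·D.
- With Q3 - Q2: δ = E - D - ω_c·D.
- Written minus consistent: D·(1 + ω_c - ω_w).

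**4. Size**

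Inputs from the plan (Section 9.2 and Table 2A): 120 participants in 8 courses (15 each), SD 4, ICC 0.10, effect of 3 points, two-sided 0.05. Assumed, because the plan gives neither: a mean drift d per period, equal in both periods, and a within-person correlation r of 0.4 / 0.6 / 0.8. Equation 1 was fitted by REML without the demographic covariates and with complete data, 600 replicates per scenario, both codings on the same data sets. Negative δ means benefit.

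| r | ω_w | ω_c | 1 + ω_c - ω_w |
|---|---|---|---|
| 0.4 | -0.40 | -0.66 | 0.74 |
| 0.6 | -0.32 | -0.43 | 0.89 |
| 0.8 | -0.19 | -0.21 | 0.98 |

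The simulated shifts per point of drift were 0.73 / 0.88 / 0.97 at d = -1 and 0.76 / 0.90 / 0.99 at d = +1. At d = -1 they were 0.77 / 0.89 / 0.97 with ICC 0 and 0.57 / 0.79 / 0.95 with ICC 0.3.

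Hand check at d = -1, no effect, r = 0.4 (D = E = -1). As written: -1 - (-0.40)(-1) = -1.40. With Q3 - Q2: -1 + 1 - (-0.66)(-1) = -0.66. The simulated means were -1.42 and -0.69.

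| Scenario (r = 0.4 / 0.6 / 0.8) | As written | Q3 - Q2 |
|---|---|---|
| No effect, d = 0: p<0.05 | 5% to 6% | 6% to 9% |
| No effect, d = -0.5: p<0.05 | 53 / 65 / 81% | 13 / 11 / 10% |
| No effect, d = -1: mean δ | -1.42 / -1.34 / -1.21 | -0.69 / -0.46 / -0.24 |
| No effect, d = -1: p<0.05 | 97 / 99 / 100% | 34 / 22 / 16% |
| Effect -3, d = +1: mean δ | -1.62 / -1.70 / -1.82 | -2.37 / -2.59 / -2.81 |
| Effect -1, d = +1: mean δ | +0.4 / +0.3 / +0.2 | -0.37 / -0.59 / -0.81 |
| Effect -1, d = +1: significant benefit | under 1% | 12 / 31 / 73% |

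With effect -3 and d = +1, p<0.05 occurs in at least 99% of runs under both codings. A separate shorter run reproduced the means, the coefficients and the pattern of rejection rates for the d = 0, d = -1 and effect -3 scenarios.

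**5. Table 2A**

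The plan does not state its method. A standard stepped-wedge variance (one course crossing over per step, fixed period effects, 15 participants per course spread over all periods) gives 2.679 / 2.990 / 2.857 for the pilot and 1.316 / 1.495 / 1.444 for the larger trial. The printed values are 2.68 / 2.99 / 2.86 and 1.32 / 1.49 / 1.44. That calculation does not use the disputed definition, so nothing suggests the table depends on it.

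**The case against.** The strongest reply is that this is a typing error which the surrounding text resolves. Four other statements point to Q3 - Q2, and the planned per-participant summaries would show a δ that did not fit them. That is probably right about the origin. It does not remove the need for correction, because the legend is the formal definition a programmer would follow.

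The second reply is that the stakes are low: Section 9.2 says the pilot is not formally powered for efficacy, Section 9.5 calls this analysis preliminary, and progression (Section 9.1) rests on attendance and on who is recruited. This stands and limits the weight of the point.

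The third is that drift and within-person correlation are assumed. This also stands. The waiting period varies in length, so equal drift per period is itself an assumption, and the simulations leave out covariates and missing questionnaires. The contradiction and the algebra do not depend on any of this.

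The fourth is that the corrected coding is not a clean 5% benchmark. In nearly all fits with Q3 - Q2 the participant variance was estimated at zero, and under drift the Pre adjustment leaves a remainder of -ω_c·D in δ. Both are true. They qualify the comparator's rejection rates, not the shift that the printed line causes, and the remainder is a separate matter.

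**Conclusion.** The concern holds. The intervention line of the Equation 1 legend is wrong as written and inconsistent with the rest of Section 9.5. Followed literally, it shifts δ by D·(1 + ω_c - ω_w) relative to the consistent coding. That is about 0.7 to 1.0 point per point of mean change over the wait at the plan's ICC of 0.10, and about 0.6 to 1.0 across ICCs of 0 to 0.3, for assumed within-person correlations of 0.4 to 0.8.

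Improvement over the wait exaggerates the benefit and raises the false-positive rate. Worsening shrinks the benefit, and an effect no larger than the drift can vanish or change sign. An effect of the plan's own 3 points would still be detected under a 1-point worsening per period, but at little more than half its size. With no mean change over the wait there is no bias. Only the preliminary efficacy analysis is touched. Confidence is high for the contradiction and the algebra; the sizes depend on the assumed drift and correlation.

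**What to change.** In the Equation 1 legend, change the intervention-period definition from Q3 - Q1 to Q3 - Q2, keeping Pre = Q2, and do so before the analysis is programmed so that it cannot look like a choice made after seeing the data. The cost is one line of text, with no new data or analysis.

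Separately and optionally, the plan could note that with Pre in the model δ still differs from (Q3 - Q2) - (Q2 - Q1) by -ω·mean(Q2 - Q1) when scores drift, and report that unadjusted contrast as a sensitivity analysis. The per-participant changes it needs are already planned under Aim 2.

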## **10 DATA COLLECTION AND QUALITY ASSURANCE**

### **10.1 Data Collection Forms**

All data will be collected through the REDCap database embedded in the Presence Care website. If a course participant does not have access to a computer or the internet, there will be an option to speak with staff and complete the information via interview, which will be entered into the Presence Care website.

### **10.2 Data Management**

All data will be entered directly into eCRFs in REDCap. The data system includes password protection and internal quality checks to identify data that appear inconsistent, incomplete, or inaccurate. Instructor logs from the MBDC classes will also be directly entered in REDCap.

## **10.3 Quality Assurance**

### **10.3.1 Training**

MBDC program instructors are operating under standard of care based on Presence Care training. Instructors will be trained on data entry in REDCap, for example documenting attendance, etc.

### **10.3.2 Quality Control Committee**

Not applicable.

### **10.3.3 Metrics**

Metrics for quality control include the following:

- Number of protocol deviations
- Number of data entry errors
- Number of technological issues with survey distribution

### **10.3.4 Protocol Deviations**

It will be the responsibility of the PI to identify, document in REDCap, and report deviations as soon as possible.

### **10.3.5 Monitoring**

The study team programmer will perform internal data quality checks on the data set provided through the Data Use Agreement with Presence Care. Should independent monitoring become necessary, the PI will provide direct access study data for the purpose of monitoring and auditing by the sponsor/funding agency, and inspection by local and regulatory authorities.

## **11 PARTICIPANT RIGHTS AND CONFIDENTIALITY**

### **11.1 Institutional Review Board Review**

This study will be using Advarra as a central IRB. Any institution considered engaged in human subject research activities will complete a local IRB application as needed to cede oversight of the project to the central IRB. Any modifications to this protocol will be reviewed and approved by the IRB.

### **11.2 Informed Consent Forms**

We request a waiver of informed consent for all aspects of this study, to include the use of electronic medical records for recruitment purposes, randomization assignment, enrollment and participation in the MDPC program, and the use of the collected program data. We offer the following justifications for the waiver of informed consent:

1. *the research involves no more than minimal risk to the subjects;*

The mailing of an informational brochure to the patient about a program of potential interest to the family involves no more than minimal risk to the subject. People receive unsolicited mail from many sources including advertisement of services they are not interested in. In addition, the MBPD program is already offered as a standard program in some places. CPs who have completed the MBDC program to-date have provided overwhelmingly positive feedback about the program and its life-changing lessons (Figure 3). There have been no reported adverse events related to participation in MBDC. The randomization component is minimal risk as well, particularly since the CP will be given the option to choose their preferred day and time if they decline the randomly assigned MBDC course. We are assessing the feasibility of randomization and do not want to withhold the MBDC program from those for whom this is not feasible. Use of the administrative data will be governed by a data use agreement.

*2. The research could not practicably be carried out without the requested waiver;*

The main purpose of this study is to assess the feasibility, acceptability, and fidelity of implementation of the Mindfulness Based Dementia Care (MBDC) program in practice. Participation is voluntary and participants can drop out at any time and are free to skip any questions during the data collection process. The centralized registration and administrative data collection process described herein is being created as a permanent part of MBDC through the Presence Care website. It would not be practicable to add research informed consent to this process as there is a possibility that the knowledge of being in a research study, or the burden of having to fill out extra paperwork would bias the feasibility, acceptability, and fidelity of implementation that we are hoping to measure.

*3. If the research involves using identifiable private information or identifiable biospecimens, the research could not practicably be carried out without using such information or biospecimens in an identifiable format;*

We require identifiable information for recruitment purposes. We could not mail without access to this identifiable information. Access to the administrative data from Presence Care will be governed by a data use agreement

*4. The waiver or alteration will not adversely affect the rights and welfare of the subjects;*

While we are requesting a waiver of informed consent for research purposes, participation in the program is completely voluntary, as is answering any of the questions in the data collection activities. Participants can stop the program at any time. We include a statement as part of the administrative data set questionnaires that: 1) answering questions is voluntary; 2) their answers may be shared in a de-

identified way with researchers. A “yield” approach for empty data fields will be used in the survey software that triggers an alert asking for, but not requiring the completion of data elements

5. *Whenever appropriate, the subjects will be provided with additional pertinent information after participation*

Information about the MBDC program is already present in each site’s memory clinic newsletters and/or in notices in clinic common areas. We plan to invite patients, CPs, and families to a virtual, community presentation of the results of the study.

Finally, please note that we do not consider the stakeholder interviews mentioned in Table 2 to be a human subjects research activity requiring consent. They consist of interviews with memory clinic leaders to discuss perspectives on recruitment for MBCD and opportunities for improving processes.

We also request a partial HIPAA waiver of authorization for the use of HealthPartners EHR data for eligibility and recruitment purposes. We offer the following justifications for the partial HIPAA waiver:

1) *Use or disclosure involves no more than minimal risk to the privacy of individuals because of the presence of at least the following elements:*

i) *An adequate plan to protect health information identifiers from improper use or disclosure,*

The HealthPartners programmer will extract PHI data from the EHR and store on a secure server in a project folder that requires individual username permission to access. ;p]

ii) *An adequate plan to destroy identifiers at the earliest opportunity absent a health or research justification or legal requirement to retain them, and*

Identifiers will be destroyed after recruitment is complete. To ensure that we do not duplicate mailings to patients, we need to retain identifiers until recruitment is complete, and cannot destroy sooner.

iii) *Adequate written assurances that the PHI will not be used or disclosed to a third party except as required by law, for authorized oversight of the research study, or for other research uses and disclosures permitted by the Privacy Rule*

PHI will not be used or disclosed to a third party except as required by law. Section 11.3 provides more detail.

2) *Research could not practicably be conducted without the waiver or alteration; and*

HealthPartners research staff will be contacting potential participants via mail to inform them of the study and therefore, potential subjects will not be available to sign a HIPAA Authorization.

**3) *Research could not practicably be conducted without access to and use of PHI.***

We require PHI information for recruitment purposes. We could not mail without access to this identifiable information.

**11.3 Participant Confidentiality**

To protect against risk of breach of confidentiality, we will use REDCap, which is a secure web-based system used for data collection and is compliant with federal regulations (21 CFR Part 11, FISMA, HIPAA, and GDPR).

To protect patient privacy, recruitment letters will be addressed to patients and mailed to the patient address. In case a patient may not be aware of a dementia diagnosis or not remember it, we will use sensitive language such as “information about a program of potential interest” and avoid statements that could cause alarm.

Information will not be released without written permission of the participant, except as necessary for monitoring by IRB, the sponsor or persons working on behalf of the sponsor (i.e. IMPACT research study staff, the DSMB and/or Safety Officer), the FDA, the NIA, and the OHRP.

**11.4 Study Discontinuation**

The study may be discontinued at any time by the IRB, the NIA, the OHRP, the FDA, or other government agencies as part of their duties to ensure that research participants are protected.

**12 ETHICAL CONSIDERATIONS**

This study will be approved by a central IRB and conducted in accordance with the Belmont Report and the Declaration of Helsinki.

**13 COMMITTEES**

Not applicable.

**14 PUBLICATION OF RESEARCH FINDINGS**

This trial will be registered at ClinicalTrials.gov, and results information from this trial will be submitted to ClinicalTrials.gov. In addition, every attempt will be made to publish results in peer-reviewed journals

